## 8.6 SFE Period (Week 52 to Week 156)

All eligible subjects must complete the Week 52 visit assessments.

Eligible subjects are allowed to roll-over to the SFE-Period up to 3 months after completion of the Week 52 assessments.

Prior to rolling over to the SFE Period, subjects will be asked to read and sign a separate informed consent form.

Telephone contacts are upon the discretion of the Investigator. Starting at Week 56, and at the discretion of the Investigator, it is recommended to contact the subject by phone at least once in between the on-site visits.

Starting at Week 64, all subjects are to visit the site approximately every 12 weeks ( $\pm 2$  weeks) for-assessments performed according to local standard medical practice, as needed, including:

- Document AEs (Note: any [possible] drug-related AE must be followed-up, at least by phone.)
- Contact IXRS
  - to register the visit and obtain next kit number at Weeks 54 and 56 for subjects receiving loading doses of study drug administration at the study site
  - to register the visit and obtain next kit number for subjects receiving study drug administration at the study site approximately Q12W during the remainder of the study
  - to indicate that the subject has withdrawn from the study, if applicable

At Week 156/SFE-WD ( $\pm 1$  week), all subjects are to visit the site for the following assessments:

- Blood sample for CRP
- BASDAI
- BASFI

- 
- ASQoL
  - Total and nocturnal spinal pain
  - PGADA
  - MRI SI joints
  - AEs
  - Contact IXRS to indicate that the subject has completed the SFE Period (Week 156/SFE WD)

### **8.7 FU visit (8 weeks after the Week 52/WD visit [ $\pm 3$ days])**

Subjects not participating in the SFE Period will attend a FU visit 8 weeks after the Week 52/WD visit ( $\pm 3$  days).

Assessments at this visit include:

- Vital signs; pulse rate, systolic and diastolic blood pressure, and temperature (respiration rate will be assessed in addition if the subject experiences an AE)
- Blood samples will be collected for hematology, biochemistry, CRP, and serum pregnancy test for women of childbearing potential
- Urine will be collected for urinalysis
- Physical examination
- Plasma for CZP concentration, anti CZP antibodies, and biomarkers
- Concomitant medication
- AEs
- Contact IXRS to indicate that subject has completed FU

### **8.8 Unscheduled visits**

It is at the Investigator's discretion to initiate an Unscheduled Visit, if deemed necessary by the Investigator for the subject's safety and well-being. At this visit, any of the following or other assessments at the Investigator's discretion may be performed depending on the reason for the visit:

- Vital signs
- Blood samples for hematology, biochemistry, other testing such as for TB or CRP
- Urine for urinalysis and/or pregnancy testing (for women of childbearing potential)
- Physical examination
- Concomitant medication
- AEs

- TB questionnaire
- Contact IXRS to indicate that subject attended an unscheduled visit

### **8.9 Alternative visit schedules after subject discontinuation of the double-blind study treatment**

Subjects who discontinue the double-blind study treatment and enter open-label treatment with CZP will be assessed 2 and 4 weeks after open-label CZP treatment has been initiated and every 12 weeks thereafter. Alternatively, subjects who discontinue the double-blind study treatment and receive other treatment (including biologics) will be assessed every 12 weeks after initiation of the other treatment. The alternative schedules for open-label CZP and other treatment can be found in [Table 5-2](#) and [Table 5-3](#), respectively. In either alternative schedule, assessments should be conducted until as close as possible to Week 52 (within  $\pm 4$  weeks), where Week 52 is relative to the original randomization at Week 0. Subjects will then be invited to the final assessment visit at Week 52.

The following assessments will be performed for subjects who are treated with open-label CZP after discontinuation of the double-blind study treatment:

- Vital signs; pulse rate, systolic and diastolic blood pressure, and temperature (respiration rate will be assessed in addition if the subject experiences an AE) at wdt Weeks 0, 2, 4, 12, 24 (and every 12 weeks [Q12W]), 52, and FU (8 weeks after Week 52 Visit)
- Blood samples will be collected for hematology, biochemistry, and CRP analyses, and urine will be collected for urinalysis at wdt Weeks 0, 12, 24 (and Q12W), 52 and FU (8 weeks after Week 52 Visit)

Note: Fasting blood samples will be collected for hematology, biochemistry, and CRP analyses at wdt Week 0 (biochemistry assessment will include the measurement of Apo A1, ApoB, lipoprotein(a), and HbA1c). At Week 52, the biochemistry assessment will include the measurement of HbA1c.

- Pregnancy test for women of childbearing potential at wdt Weeks 0, 52 (urine testing), and FU (serum testing)
- Physical examination at wdt Weeks 0, 4, 12, 24 (and Q12W), 52, and FU
- Extra-articular assessments at wdt Weeks 12, 24 (and Q12W), and 52
- TB test at wdt Week 52 only
- TB questionnaire at wdt Weeks 0, 12, 24 (and Q12W), and 52
- SF-36, AsQoL, MOS Sleep Scale, EQ-5D, and MASES at wdt Weeks 0, 12, 24 (and Q12W), and 52
- BASMI & spinal mobility, BASFI, total and nocturnal spinal pain, swollen and tender joint counts, BASDI, Patient's Global assessment, and Investigator's AS assessment at wdt Weeks 0, 4, 12, 24 (and Q12W), and 52
- Plasma for CZP concentration, anti-CZP antibodies, and for biomarkers at wdt Weeks 0, 4, 12, 24 (and Q12W), 52, and FU

- 
- Gene expression and proteomics at wdt Week 52 only
  - Concomitant medication at wdt Weeks 0, 2, 4, 12, 24 (and Q12W), 52, and FU
  - AEs at wdt Weeks 0, 2, 4, 12, 24 (and Q12W), 52, and FU
  - IXRS (for treatment assignment) at wdt Weeks 0, 2, 4, 12, 24 (and Q12W), 52, and FU
  - CZP administration at wdt Weeks 0, 2, 4, 6, 8, 10, 12, 14, 16, 18, 20, 22, 24, and every 2 weeks thereafter, until Week 52. Loading dose of CZP 400mg at Weeks 0, 2, and 4 must be administered by dedicated site-staff
  - Telephone contact will occur every 4 weeks after the on-site visit at the discretion of the investigator

The following assessments will be applied for subjects who receive an alternative study assessment with other treatment (including biologics) after discontinuation of the double-blind study treatment:

- Blood samples will be collected for hematology and biochemistry analyses, and urine will be collected for urinalysis at wdt Week 0. C-reactive protein analyses will be performed at wdt Weeks 0, 12, 52, and FU

Note: Biochemistry assessment will include the measurement of HbA1c at wdt Week 0

- Physical examination at wdt Week 0 and FU.
- BASDAI, BASFI, total and nocturnal spinal pain, Patient's Global assessment, and Investigator's AS assessment at wdt Weeks 0, 12, and 52
- Swollen and tender joint counts at wdt Week 52 only
- Plasma for CZP concentration, anti-CZP antibodies, and for biomarkers at wdt Weeks 0, 12, and FU
- Concomitant medication at wdt Weeks 0, 12, 24 (and Q12W), 52, and FU
- AEs and IXRS (for the registration of visits) at wdt Week 0, 12, 24 (and Q12W), 52, and FU
- Other treatment administration at wdt Week 0. For Week 12 and 24 (and Q12W) the regimen of the particular medicine should be followed. If the Investigator chooses to withdraw the subject, the local guidelines on initiation and monitoring of the particular treatment should be followed.
- Telephone contact will occur every 4 weeks after the on-site visit at the discretion of the Investigator

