MASES	X							X						X	X	

Continue W24 assessments every 12 weeks until as close as possible to W52/WD of the original visit schedule. Subject will then be invited to the final assessment visit at W52/WDe

**Table 5-2: Schedule of alternative study assessment with CZP - after subject discontinuation of the double-blind study treatment**

Visit #	1 wdt	2 wdt	3 wdt	4 wdt	6H	8H	10H	12 wdt	14H	16H	18H	20H	22H	24 and Q12W wdt	52/WD a	FU a
Week Protocol Activity	0	2	4													
Total and nocturnal spinal pain	X		X	X										X		
Swollen and tender joint counts	X		X	X										X		
Patient's Global assessment	X		X	X										X		
Investigator's AS assessment	X		X	X										X		
CZP plasma concentration/ anti-CZP Abs/ Biomarker	X		X	X										X		X
Gene expression and proteomics j															X	
Telephone contact k					X					X						
Prior and Concomitant medication	X	X	X	X										X		X
AEs	X	X	X	X										X		X
IXRS	X	X	X	X										X		X
CZP administration sc	X l	X l	X	X	X	X	X	X	X	X	X	X	X	X m		

**Table 5-3: Schedule of alternative study assessment with other treatment (including biologics) - after subject discontinuation of the double-blind study treatment**

Visit #	1 wdt	2 wdt	3 wdt		
Week	0	12	24 and Q12W		FU a
Protocol Activity					52/WD
Hematology/urine/biochemistry	X b,c				
CRP	X	X			X
Pregnancy testing e	X				X
PE	X				X
BASDAI	X	X			
BASFI	X	X			
Total and nocturnal spinal pain	X	X			
Swollen and tender joint counts					
Patient's Global assessment	X				
Investigator's AS assessment	X	X			
CZP plasma concentration/anti-CZP Abs/ Biomarker	X	X			X
Prior and Concomitant medication	X	X	X		X
AEs	X	X	X		X
IXRS e	X	X	X		X
Other treatment administration	X f	Follow the regimen of the particular alternative treatment. Telephone contact to be performed on the discretion of the Investigator			
Continue W24 assessments every 12 weeks until as close as possible to W52/WD of the original visit schedule. Subject will then be invited to the final assessment visit at W52/WD ±4 weeks. d					

**Table 5-3: Schedule of alternative study assessment with other treatment (including biologics) - after subject discontinuation of the double-blind study treatment**

Week	Visit #	1 wdt	2 wdt	3 wdt	Continuation W24 assessment	FU a
Protocol Activity		0	12	24 and Q12W	52/WD	FU a

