Abs=antibodies; AE=adverse event; Abs=antibodies; AE=adverse event; BASDAI=Bath Ankylosing Spondylitis Disease Activity Index; BASFI=Bath Ankylosing Spondylitis Functional Index; CRP=C-reactive protein; CZP=certolizumab pegol; eCRF=electronic case report form; FU= Follow-Up; H=home, no site visit; IXRS=Interactive Response System; PE=physical exam; Q12W=every 12 weeks; W=Week; WD=Withdrawal, wdt=withdrawal treatment  
 Note: All weeks are ±3 days compared to Baseline. Week 0 of the alternative schedule starts 2 weeks after the last dose of the double-blind study treatment.  
 Note: Local guidelines on initiation and monitoring of the particular treatment should be followed.

a FU: 8 weeks after Week 52/WD visit.

b Subjects will be encouraged to be in fasting condition at the time the subject shifts to alternative treatment, for Apo A1, ApoB, and lipoprotein(a) assessments.  
c HbA1c will be measured at wdt Week 0.

d If the last Q12W assessment for a subject who discontinues study treatment is ≤4 weeks before the final assessments visit at Week 52/WD, the assessment should be cancelled and the subject should instead be invited to undergo the final assessments visit at Week 52/WD (the Week 52/WD visit is to be scheduled 52 weeks [±3 days] after Baseline).

e For registration of visit only. Interactive Response System won't assign any open treatment medication.

f Follow the regimen of the particular alternative treatment. Arrange for additional site visits for administration and record the treatment in the Concomitant Medication eCRF as appropriate.

g Pregnancy testing must be carried out for women of childbearing potential and will be a serum test at the FU visit and a urine test (dipstick) at wdt Week 0 and Week 52/WD visit.

At any time during the study course, but preferably not before Week 12, the Investigator may discontinue the double-blind study treatment and start open-label treatment with either CZP (which will be provided free of charge by UCB) or an alternative drug (eg, other treatment [including biologics]).

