#### 9.1.4 ASQoL

The ASQoL, a validated disease-specific 18-item questionnaire, has been developed specifically for measuring HRQoL in subjects with AS (Doward et al, 2003). The ASQoL has been used and has shown to be responsive in axSpA (Barkham et al, 2009; Haibel et al, 2008). The ASQoL score ranges from 0 to 18 with higher score indicating worse HRQoL. A change of 1.8 points, which represents 10% of the possible score range, has been used as the minimal clinically important difference (MCID) criteria to guide the interpretation of ASQoL score changes in previous trials with a TNFi (van der Heijde et al, 2009; Davis et al, 2007). A change in ASQoL score of 2 points (ie, 10% of the total score range) will be used as the MCID to guide the interpretation of ASQoL score changes (see Appendix 18.4).

The ASQoL assessments per visit are described in Table 5–1, Table 5–2, and Table 5–6.

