#### **9.1.6 BASFI**

The BASFI is a validated disease-specific instrument for assessing physical function (van der Heijde et al, 2005; Calin et al, 1994). The BASFI comprises 10 items relating to the past week. The NRS version will be used for the answering options of each item on a scale of 0 (“Easy”) to 10 (“Impossible”) (van Tubergen et al, 2015 and van Tubergen et al, 2002a). The BASFI is the mean of the 10 scores such that the total score ranges from 0 to 10, with lower scores indicating better physical function. The MCID used to interpret scores is 7mm on a 0 to 100mm VAS or 17.5% of the Baseline score (Pavy et al, 2005); an MCID of 1 unit will be used for the NRS version (see Appendix 18.6).

The BASFI assessments per visit are described in Table 5–1, Table 5–2, Table 5–3, and Table 5–6.

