For the secondary efficacy variable “number of subjects with AU or new AU flares through Week 52,” missing values should only occur in the unlikely case that a subject does not have any post-Baseline AU assessments performed. Therefore, sensitivity analyses for this variable will focus on analyses adjusting for exposure time at risk such as event rate, incidence rate, and confidence interval.

The sensitivity analyses of secondary continuous efficacy variables (the change from Baseline in BASDAI and BASFI at Weeks 12 and 52, and the change from Baseline in the SI joint SPARCC score at Week 12, change from Baseline in ASQoL at Week 52, and change from Baseline in nocturnal spine pain at Week 52) will be as follows:

- Including observed data at Week 52: As described for the primary efficacy variable.
- MI: As described for the primary efficacy variable.
- Observed case analysis: As described for the primary efficacy variable.

- LOCF

Missing data for the other efficacy variables described in Section 14.5 will be handled as follows:

- With imputation: Non-responder imputation for binary variables and LOCF for continuous variables (as described in Section 14.5)
- Observed case analysis: As described for the primary efficacy variable.

Additionally, algorithms for imputing missing or partial dates for safety evaluations will be detailed in the SAP.

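### The visit schedule for subjects who switch to other treatment omits ASQoL, although Section 8.5 lists it for every Week 52 visit and Section 14.8 plans an observed-data Week 52 analysis of it

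*Protocol*

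**What the plan says.** **ASQoL collection**

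- Section 8.9, subjects on other treatment: "BASDAI, BASFI, total and nocturnal spinal pain", together with the patient's and the investigator's global assessments, at Weeks 0 and 12 of the alternative schedule and at Week 52. CRP and joint counts are also scheduled at Week 52. ASQoL is not listed there or in Table 5-3.
- Section 8.9, subjects on open-label CZP: "SF-36, AsQoL, MOS Sleep Scale, EQ-5D, and MASES at wdt Weeks 0, 12, 24 (and Q12W), and 52".
- Section 9.1.4: "The ASQoL assessments per visit are described in Table 5–1, Table 5–2, and Table 5–6". Table 5-3 is not named. Compare Section 9.1.6: "The BASFI assessments per visit are described in Table 5–1, Table 5–2, Table 5–3, and Table 5–6".
- Section 8.5, the Week 52/WD visit: ASQoL is on the list, and no group is exempted.

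**ASQoL analysis**

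- Section 14.2 places ASQoL change at Week 52 ninth of eleven tests in both hierarchies.
- Section 14.8 names "change from Baseline in ASQoL at Week 52" among the continuous secondary variables that get an analysis including observed Week 52 data, carried out as for the primary variable. For the primary variable this means using Week 52 data whether or not the subject is still on randomized treatment, and treating those still missing as non-responders.

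**Timing of the Week 52 visit in Table 5-3**

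- Table cell: "final assessment visit at W52/WD ±4 weeks".
- Footnote d, attached to that cell: "the Week 52/WD visit is to be scheduled 52 weeks [±3 days] after Baseline".

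**The concern.** An observed-data analysis differs from one that discards or replaces post-discontinuation values only through subjects who stopped double-blind treatment and were still followed. Those subjects take one of two routes: open-label CZP or another treatment. If ASQoL is collected on the first route and not on the second, the analysis sees only part of the discontinuers, and the part is selected by the investigator's choice of next therapy. The plan then needs a rule for the rest, and the rule it borrows was written for a binary endpoint.

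ASQoL and nocturnal spinal pain entered the testing sequence together under Amendment 4. Nocturnal pain is on the other-treatment schedule; ASQoL is not.

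The Week 52 window is a separate inconsistency in the same table. A site reading the cell alone would accept a far wider visit date than a site reading the footnote.

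**Working it through.** The protocol gives no figure on this point to reproduce, so the check is mainly a comparison of passages.

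**1. Is ASQoL scheduled at Week 52?**

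| Group | Section 8.5 | Section 8.9 and its table | Section 9.1.4 |
|---|---|---|---|
| Still on double-blind treatment | Yes | Not applicable | Yes (Table 5-1) |
| Switched to open-label CZP | Yes | Yes (Table 5-2) | Yes (Table 5-2) |
| Switched to other treatment | Yes | No (Table 5-3) | No (Table 5-3 not named) |

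The last row is the conflict. It is not an artefact of a broken table: the running text of Section 8.9 and the cross-reference in Section 9.1.4 agree with Table 5-3, while the sections on BASDAI, BASFI, PGADA and spinal pain all do refer to Table 5-3.

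**2. Which ASQoL analyses would use the missing values?**

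- Main analysis, test 9 (Section 14.4): reference-based multiple imputation replaces values after discontinuation in both arms. Not affected.
- Multiple imputation under MAR (Section 14.8): data after discontinuation are treated as missing. Not affected.
- Observed case (Section 14.8): data after discontinuation are excluded. Not affected.
- Including observed data at Week 52 (Section 14.8): uses these values. Affected.

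LOCF is listed for these variables without detail. The observed-data analysis is therefore the only one that clearly draws on ASQoL collected after a switch.

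**3. Does the fallback work?** ASQoL runs from 0 to 18 (Section 9.1.4) and is analysed as a change from Baseline. Non-responder status cannot be entered as a value of that change, so as written the missing subjects have no usable rule.

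**4. How many subjects?** The protocol states no rate of switching to other treatment. Taking a share *s* of the 300 randomized as an assumption, the number without a Week 52 ASQoL under Section 8.9 is 300 × *s*:

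- *s* = 5%: 300 × 0.05 = 15
- *s* = 10%: 300 × 0.10 = 30
- *s* = 20%: 300 × 0.20 = 60

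**5. What is still observable for this group?** ASDAS needs BASDAI items 2, 3 and 6, PGADA and CRP. ASAS40 needs PGADA, total spinal pain, BASFI and BASDAI items 5 and 6. All are scheduled at Week 52 on this route, as is nocturnal pain.

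**6. The window.** ±4 weeks is ±28 days, or 2 × 28 + 1 = 57 calendar days. ±3 days is 2 × 3 + 1 = 7 calendar days. The ratio is 57 / 7, about 8. The table note, footnote d and the heading of Section 8.5 say ±3 days; Section 5.2 asks for the originally planned Week 52 date. Sections 5.1.1 and 8.9 also mention ±4 weeks, but there it governs how long the 12-weekly visits go on before the Week 52 visit. Only the Table 5-3 cell attaches it to the Week 52 visit itself, and the matching cell of Table 5-2 carries no such window.

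**The case against.** The strongest reply is that little depends on this. Test 9 imputes everything after discontinuation, so ASQoL collected from switchers would never enter the hierarchy. The primary composite already counts discontinuers as non-responders. Subjects on open-label CZP are discontinuers too and do complete ASQoL at Week 52. All of this stands and sets the size of the point.

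It can also be said that Section 8.5 lists ASQoL for everyone, so the data may be collected after all. That is fair: a reader might infer that every other-treatment subject is certain to lack ASQoL, and the protocol does not support that certainty. It does leave the site with two lists that disagree, the one specific to this group being the one without ASQoL.

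On timing, a reader might infer that switchers have a Week 48 to 56 window, and that a visit outside ±3 days would be set to missing and counted as non-response. The documents do not support either step. Footnote d cancels a 12-weekly visit falling within 4 weeks before Week 52: a switch at Week 24 gives visits at Weeks 36 and 48, and the Week 48 visit is dropped in favour of Week 52. A switch at Week 20 gives a visit at Week 56, after the planned Week 52 date. No passage removes off-window efficacy data, and analysis windows commonly belong to the SAP, which is not shown. What remains is one table cell at odds with its own footnote.

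**Conclusion.** The point holds in a limited form. Section 8.9, Table 5-3 and Section 9.1.4 conflict with Section 8.5 on ASQoL for subjects who switch to other treatment. If Section 8.9 is followed, the observed-data Week 52 analysis planned in Section 14.8 has no ASQoL from this group and no workable rule for it.

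The effect reaches one sensitivity analysis of the ninth-ranked variable. The main ASQoL test, the primary composite and the ASDAS, ASAS40, BASDAI, BASFI and spinal pain data are untouched. It would be too strong to say that the analysis loses exactly the subjects it was designed for, because open-label CZP switchers contribute.

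The count of 15 to 60 subjects rests on an assumed 5% to 20% switch rate over both arms; the conflict between the sections does not. The ±4-week cell is a separate inconsistency with no demonstrated effect on any result.

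**What to change.** 1. Add ASQoL at Week 52 to Table 5-3 and to the other-treatment list in Section 8.9, and name Table 5-3 in Section 9.1.4, so that all three agree with Section 8.5.
2. In Section 14.8, replace the non-responder fallback for continuous variables in the observed-data analysis with a rule that suits a score, for example the reference-based multiple imputation already planned. Section 14.10 records that the study was fully enrolled by Amendment 4, so some Week 52 visits may already have passed; for those subjects this step is the only remedy.
3. Reconcile the window in the Table 5-3 cell with footnote d, the table note, Section 5.2 and Section 8.5.

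The cost is one 18-item questionnaire at a visit that already takes place, on the site tablet that Section 13.2.1 already uses for ASQoL, BASDAI, BASFI, PGADA and spinal pain, plus text edits. The downside is a few minutes of subject time.

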## 9 ASSESSMENT OF EFFICACY

Most of these tools have been used in AS studies but early data support their use in axSpA as well (Barkham et al, 2009; Haibel et al, 2008).

## 9.1 Assessment of efficacy variables

### 9.1.1 ASDAS

The ASDAS is comprised of a number of assessments which are scored by the subject and physician and multiplied by a proven formula (van der Heijde et al, 2009) as listed:

0.121 x Back pain (BASDAI Q2 result, see Section 9.1.5)

0.058 x Duration of morning stiffness (BASDAI Q6 result)

0.110 x PGADA (see Section 9.1.13)

0.073 x Peripheral pain/swelling (BASDAI Q3 result)

0.579 x (natural logarithm of the (CRP [mg/L] + 1))

Back pain, PGADA, duration of morning stiffness, peripheral pain/swelling and fatigue are all assessed on a numerical scale (0 to 10 units) (Lukas et al, 2009).

The variables related to ASDAS disease activity are defined as follows:

- ASDAS-Inactive Disease (ASDAS-ID): ASDAS <1.3
- ASDAS-Low Disease (ASDAS-LD): ASDAS  $\geq$ 1.3, <2.1
- ASDAS-High Disease Activity (ASDAS-HD): ASDAS  $\geq$ 2.1,  $\leq$ 3.5
- ASDAS-very High Disease Activity (ASDAS-vHD): ASDAS >3.5

The variables related to ASDAS improvement are defined as follows:

- ASDAS-Clinically Important Improvement (ASDAS-CII): ASDAS reduction (improvement) of  $\geq$ 1.1 relative to Baseline
- ASDAS-Major Improvement (ASDAS-MI): ASDAS reduction (improvement) of  $\geq$ 2.0 relative to Baseline

The ASDAS will be calculated at Screening, Baseline, Weeks 2, 4, 8, 12, 16, 20, 24, 28, 32, 36, 40, 44, 48, 52/WD, and Week 156/SFE-WD.

